16.1.2.3 Excretion Parameters

• PK Parameters for GBT021601 and ¹⁴C-GBT021601 total radioactivity as defined in Table 5.

EDSREP 009 T 01 G Page 15 of 30

Table 5 PK parameters for excretion

Parameter	Description	Analyte
CLR	Renal clearance	GBT021601
Ae _{urine}	Cumulative amount of drug excreted in urine at each interval	¹⁴ C-GBT021601 Total Radioactivity, GBT021601
fe _{urine}	Fraction of the dose administered excreted in urine (%) at each interval	¹⁴ C-GBT021601 Total Radioactivity, GBT021601
Ae _{feces}	Cumulative amount of drug excreted in feces at each interval	¹⁴ C-GBT021601 Total Radioactivity
fe _{feces}	Fraction of the dose administered excreted in feces (%) at each interval	¹⁴ C-GBT021601 Total Radioactivity
Ae _{vomit}	Cumulative amount of drug excreted in vomitus (if applicable)	¹⁴ C-GBT021601 Total Radioactivity
fe _{vomit}	Fraction of the dose administered excreted in vomitus (%), if produced	¹⁴ C-GBT021601 Total Radioactivity
Ae _{total}	Total amount of drug excreted in urine and feces	¹⁴ C-GBT021601 Total Radioactivity
fe _{total}	Total fraction of the dose administered excreted in urine and feces	¹⁴ C-GBT021601 Total Radioactivity

The administered dose is calculated by multiplying the amount (400 mL) of the solution given by the radioactivity per mL of the solution.

The radioactivity per mL solution is calculated by multiplying the label claim (0.185 kBq/mL) by the % radioactivity results (98.5%) of the product (which is established by the QC department):

Administered dose =
$$400 \text{ mL} * 0.185 (kBq/mL) * 0.985 = 72.89 kBq$$

16.2 Pharmacokinetic Summaries

16.2.1 Pharmacokinetic Concentrations

Individual whole blood, plasma and concentration data will be presented together with descriptive statistics by time point for each analyte. Participants excluded from the PK analysis set will be flagged.

Whole blood, plasma and concentrations that are BQL will be set to zero in the computation of descriptive statistics of concentration values. Descriptive statistics (number of subjects, arithmetic mean, geometric mean, standard deviation (StDev), coefficient of variation, geometric coefficient of variation, median, min, and max) will be used to summarize the whole blood, plasma and concentrations at each scheduled time point. If over two thirds of the participants at a specific time point have values BQL then the descriptive statistics will not be presented, with the exception of n, min (<LLOQ) and max.

Linear and semi-logarithmic plots of the arithmetic mean with error bars whole blood, plasma and concentrations by scheduled sampling time will be provided. These plots are planned to show time in days, but might be adjusted to another time unit based on the data. The plots will match the summary table results and will not have an observation at a given time point if more than two thirds of the participants have values ROI

Linear and semi-logarithmic plots of the individual whole blood, plasma and concentration by actual sampling time will be provided by participant. These plots will show time in hours. Individual plots will use the BQL handling procedure described below for Pharmacokinetic Parameters.

EDSREP 009 T 01 G Page 16 of 30

Statistical Analysis Plan GBT2180A-2180AX Protocol: GBT021601-013

Version Date: 01-May-2023

Linear and semi-logarithmic spaghetti plots of the (combined) individual whole blood, plasma and concentrations by actual sampling times will be provided. The full profile of the treatment will be presented in one plot. These plots will show time in hours. Spaghetti plots will use the BQL handling procedure described below for Pharmacokinetic Parameters.

Time deviations from planned dosing (only those not equal to zero) and comments will be listed.

16.2.2 Whole Blood CC to Plasma Ratios

Individual values of the ratios will be presented together with descriptive statistics by time point for the ratio of CCI to whole blood or plasma for ¹⁴C-GBT021601 Total Radioactivity

16.2.3 Pharmacokinetic Parameters

PK parameters will be estimated using non-compartmental methods with WinNonlin® and additional computations may be performed in SAS.

The whole blood, plasma and CCI for GBT021601 and ¹⁴C-GBT021601 Total Radioactivity will be estimated from the concentration-time profiles. In estimating the PK parameters, BQL values at the beginning of the profile will be set to zero. BQL values that occur after the first quantifiable point will be considered missing. Values that are embedded between BQLs, or quantifiable values occurring after 2 or more BQLs, will be set to missing at the discretion of the pharmacokineticist. All concentration values reported as no results (not collected or not determined (ND)) values will be treated as missing. Actual sampling times, rather than scheduled sampling times, will be used in all computations involving sampling times.

Descriptive statistics (number of participants, mean, geometric mean, standard deviation, coefficient of variation, geometric coefficient of variation, median, minimum, and maximum) will be used to summarize the calculated PK parameters for GBT021601 and Total Radioactivity. For 14 C-GBT021601 Individual plasma PK parameters will be presented together with descriptive statistics. For t_{max} , only median, min and max will be presented.

Only data points that describe the terminal elimination log-linear decline will be used in the regression equation for calculation of λ_z ; C_{max} and any data point in the distribution phase are not included in the calculation. A minimum of 3 points will be used for determination of K_{el} . A general rule of adjusted $R^2 \geq 0.80$ will be considered as acceptable for calculation of K_{el} . If adjusted R^2 falls below 0.80, then λ_z will be reported as Not Determined (ND) and that participant's K_{el} , $t_{1/2}$, CL/F, V_z/F and $AUC_{0-\text{inf}}$ will be reported in the appropriate listings but will be flagged and excluded from descriptive summaries and statistical analysis.

16.2.4 Pharmacokinetic Amounts Excreted

Individual excretion values will be presented together with descriptive statistics by interval and for each analyte and matrix (ie, urine, feces and total).

Descriptive statistics (number of participants, arithmetic mean, geometric mean, standard deviation, coefficient of variation, median, min, and max) will be used to summarize the amounts excreted for GBT021601 and ¹⁴C-GBT021601 at each scheduled time interval.

EDSREP 009 T 01 G Page 17 of 30

Statistical Analysis Plan GBT2180A-2180AX Protocol: GBT021601-013

Version Date: 01-May-2023

The arithmetic mean values of the cumulative amount excreted in % of the dose in urine, feces and total (urine + feces) versus time (last time point of the interval) will be presented.

Individual plots showing the cumulative amount excreted in % of the dose for all participants versus time (last time point of the interval) in urine, feces and total will be presented.

17.0 Safety Analyses

17.1 Safety Variables

The following safety variables will be summarized:

- Adverse Events (AEs)
- Vital Signs
 - Supine Blood Pressure
 - Systolic Blood Pressure (SBP)
 - Diastolic Blood Pressure (DBP)
 - Heart rate
 - Body temperature
 - Respiration rate
- Electrocardiograms (ECG)
 - o Heart Rate
 - PR Interval
 - o QRS Duration
 - o QT Interval
 - o QTcF (Fridericia) Interval
- Clinical Laboratory Evaluations
 - Clinical Chemistry
 - Hematology
 - Urinalysis
 - Coagulation
- Physical Examination

17.1.1 Adverse Events

All AE summaries will include only treatment emergent adverse events (TEAEs). TEAE are those which occur (or worsen) after the dose of study drug during the on-treatment period, defined as the period after the dose of study drug and before the minimum of (Study Day 56, study discontinuation). Day 56 has been chosen for this purpose based on the half-life of GBT021601. All AEs (including non-treatment-emergent events) recorded on the eCRF will be listed, where non-TEAEs will be flagged.

A summary (overview) table with numbers, events and percentages of participants reporting TEAEs, TEAEs related to study drug (related/unrelated), TEAEs by severity (mild, moderate, severe, life-threatening, or death), serious AEs (SAEs), and participants who discontinued the study due to an AE will be provided.

A breakdown of the number of TEAEs, number and percentage of participants reporting each TEAE, categorized by body system and preferred term coded according to MedDRA (Version 25.0), will be presented. Counting will be done by participant (participants will be counted once within each body system or preferred term) and by event.

One such table will be presented for all TEAEs. Another table like this will be presented for TEAEs considered to be related to the study medication. TEAEs' relationship to study drug is categorized as 'related' or 'not related'.

Lastly, one such table for all TEAES by severity (categories as recorded in the eCRF: Grade 1 mild, Grade 2 moderate, Grade 3 severe, Grade 4 life-threatening, or Grade 5 death), will be provided.

A listing of AEs leading to study discontinuation will be provided.

EDSREP 009 T 01 G Page 18 of 30

The following missing data will be imputed as defined (will not be presented in listings):

- Missing AE start and / or end times for the calculation of onset and duration will be assumed to be at 00:01 for a start time and 23:59 for end times
- Missing AE severity or relationship will be assumed to be severe or related, respectively
- Missing AE start date/times for the determination of treatment emergence will be assumed to occur during on-treatment period unless partial date/time documents the AE as happening prior to treatment

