- h. For females only: serum pregnancy test is required at screening only; urine pregnancy test at all other visits, with serum confirmation if positive.
- i. Clinical safety laboratory (including hematology, serum chemistry, and urinalysis) will be obtained at screening and on Days -1, 7, 28, 84, and 206 (EoS/ET).
- j. Creatinine clearance (CL_{cr}) will be calculated at screening using the Chronic Kidney Disease Epidemiology Collaboration (CKD-EPI) formula.
- cc. [REDACTED]
- l. Whole blood and plasma samples for PK of GBT021601 and total radioactivity will be taken at predose (within 60 minutes prior to GBT021601 dosing), and at 0.25, 0.5, 1, 2, 3, 4, 6, 8, 12, 24 (Day 2), 48 (Day 3), 72 (Day 4), 96 (Day 5), 144 (Day 7), 168 (Day 8), 312 (Day 14), 480 (Day 21), and 648 hours (Day 28) postdose. Additional samples will be obtained on Days 35, 42, 56, 70, 84, 98, 112, 136, 150, 178, and 206 (depending on if criteria for ending collection of urine and feces are met [see Footnote a], collection of samples may be ended prior to Day 206). Collections up to and including the 8 hours postdose sample will be collected after a participant has rested at least 5 minutes in the supine position. CCI [REDACTED]

CCI

n.

Whole blood and plasma samples for metabolite identification will be collected at predose and 1, 2, 8, 12, 24 (Day 2), 48 (Day 3), 72 (Day 4), 96 (Day 5), 120 (Day 6), 144 (Day 7), 168 (Day 8), 312 (Day 14), 480 (Day 21), and 648 hours (Day 28) hours postdose. Collections up to and including the 8 hours postdose sample will be collected after a participant has rested at least 5 minutes in the supine position. Whole blood and plasma samples for metabolite identification will also be collected at the visits on Days 84 (1992 hours postdose), 98 (2328 hours), 112 (2664 hours), 136 (3240 hours), 150 (3576 hours), 178 (4248 hours), and 206 (4920 hours; EoS/ET).

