3.5.1.2.1 Adverse Events

Adverse events will be recorded from signing the ICF until completion of the EoS/ET visit. Any clinically significant observations, as determined by the Investigator, in results of clinical laboratory, 12-lead ECGs, vital signs, or physical examinations will be recorded as AEs.

A TEAE is defined as any event not present prior to administration of the study drug or any event already present that worsens in either severity or frequency following exposure to the study drug.

An AE that occurs prior to administration of the study drug will be considered a pretreatment AE.

At several time points before and after drug administration, participants will be asked nonleading questions to determine the occurrence of AEs. Participants will be asked in general terms about any AEs at regular intervals during the study. In addition, all AEs reported spontaneously during the course of the study will be recorded. All answers will be interpreted by the Investigator using the most recent version of the MedDRA (ie, Medical Dictionary for Regulatory Activities) for AEs and will be recorded in the eCRF as reported terms.

The Investigator is responsible for evaluating all AEs, obtaining supporting documents, and ensuring that documentation of the event is complete. Details of each reported AE must include, at minimum, severity, relationship to study drug, duration, and outcome. All serious and non-serious AEs must be followed up until they are resolved or stabilized, or until reasonable attempts to determine resolution of the event are exhausted.

The severity of AEs will be graded using the most recent version of the Common Terminology Criteria for Adverse Events (CTCAE; see [Section 8.2.1](#)) 5-point scale: mild (Grade 1), moderate (Grade 2), severe (Grade 3), life-threatening (Grade 4), or death (Grade 5). The relationship between the AEs and the study drug will be indicated as related or not related. Details on rating the severity of AEs and relationship to study treatment are given in [Appendix 8.2](#).

Pregnancy of female participants and female partners of male participants will be monitored along with follow-up, if warranted (see Appendix 8.3).

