7.0 Overview of Planned Analysis

7.1 Changes from Protocol

The % Hb occupancy (at C_{max}) was added as a PK parameter.

The protocol states "Concentrations of total radioactivity in blood and excreta will be assayed weekly during the 30-day confinement phase and thereafter within 3 days of the 24-hour collections." However, blood and plasma will not be assayed weekly for concentrations of total radioactivity during the 30-day confinement phase. Only excreta will be assayed weekly for total radioactivity during the 30-day confinement phase, as described in the Protocol Clarification Memo dated 27-Oct-2022.

The definition of treatment emergent adverse events (TEAEs) has been updated compared to the protocol. TEAE are those which occur (or worsen) after the dose of study drug, consistent with the protocol text. Additionally, AEs need to take place during the on-treatment period, defined as the period after the dose of study drug and before the minimum of (Study Day 56, study discontinuation), to be considered as TEAEs. Day 56 has been chosen for this purpose based on the half-life of GBT021601.

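### AE summary tables stop before Study Day 56 although AEs are recorded to EoS/ET (up to Day 206), and the missing-date rule does not apply the same cut-off

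*SAP*

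**What the plan says.** Protocol 3.5.1.2.1 sets the collection period: "Adverse events will be recorded from signing the ICF until completion of the EoS/ET visit". It then says "A TEAE is defined as any event not present prior to administration of the study drug", or one already present that worsens after exposure, and gives no end date. The same section provides that clinically significant observations "in results of clinical laboratory, 12-lead ECGs, vital signs, or physical examinations will be recorded as AEs".

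The SAP narrows this. Section 17.1.1 says "All AE summaries will include only treatment emergent adverse events (TEAEs", and limits these to an on-treatment period "defined as the period after the dose of study drug and before the minimum of (Study Day 56, study discontinuation". Section 7.1 declares this as a change from the protocol and gives the reason: "Day 56 has been chosen for this purpose based on the half-life of GBT021601". No exception is made for related or serious events.

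For missing start dates, 17.1.1 says the AE "will be assumed to occur during on-treatment period unless partial date/time documents the AE as happening prior to treatment".

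SAP 5.2.1 names the occurrence and severity of AEs as a secondary endpoint, without a time limit. According to Appendix 3, Tables 14.3.1.1 to 14.3.1.4 all present TEAEs.

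**The concern.** The study follows participants for up to seven months because the drug is eliminated slowly, yet the tables reporting its safety endpoint cover less than the first two months. A related AE starting on Day 60 would not appear in the table of related events. An SAE on Day 100 would be in the SAE listing (Table 14.3.2.2) but not in the summary counts. A clinically significant laboratory or vital-sign finding at Day 84 or Day 206 would become an AE under the protocol and then not be counted.

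With 8 to 10 participants, one participant left out changes an incidence by 10 to 12.5 percentage points (1/10 to 1/8). A reader who wants incidence over the whole follow-up would have to rebuild it by hand from the listings.

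The missing-date rule is a separate defect. It excludes an AE only when the partial date shows onset before treatment, so two AEs from the same time can be classified differently solely because one has an incomplete date.

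**Working it through.** **Inputs**
- Cut-off: Study Day 56 (SAP 7.1 and 17.1.1).
- Day numbering: post-dose study day = date − dose date + 1 (SAP 9.2.3).
- Half-life: about 28 to 30 days (SAP 6.0).
- 24-hour visits: Days 35, 42, 56, 70, 84, 98, 112, 136, 150, 178 and 206 (Protocol 3.1.3).
- EoS: Day 206, or 7 (±3) days after the last 24-hour visit if collection ends earlier (Protocol 3.1.3).
- Safety laboratory: "will be obtained at screening and on Days -1, 7, 28, 84, and 206 (EoS/ET" (Protocol Table 1, footnote i).
- Vital signs after Day 2: Days 35, 84 and 206 (Protocol Table 1, footnote e).

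**The Day 56 figure.** Elapsed time is 56 − 1 = 55 days. In half-lives this is 55/28 = 1.96 or 55/30 = 1.83. The SAP does not state the multiple it used; 2 × 28 = 56 suggests about two half-lives, but that is an inference. If decline is mono-exponential (an assumption), the fraction of the terminal-phase level remaining is 2^(−55/28) = 25.6% or 2^(−55/30) = 28.1%. For comparison, Protocol 8.3 keeps pregnancies reportable to at least 140 days after dosing, which is 140/30 = 4.7 to 140/28 = 5.0 half-lives.

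**Share of post-dose time outside the tables** = (EoS − 56)/(EoS − 1), and zero if EoS is before Day 56. EoS is taken as the last 24-hour visit + 7 days, except for Day 206 itself.

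| Last 24-hour visit | EoS day | Share left out |
|---|---|---|
| 35 | 42 | 0% |
| 42 | 49 (52 with the +3 day window) | 0% |
| 56 | 63 | 7/62 = 11.3% |
| 70 | 77 | 21/76 = 27.6% |
| 84 | 91 | 35/90 = 38.9% |
| 98 | 105 | 49/104 = 47.1% |
| 112 | 119 | 63/118 = 53.4% |
| 136 | 143 | 87/142 = 61.3% |
| 150 | 157 | 101/156 = 64.7% |
| 178 | 185 | 129/184 = 70.1% |
| 206 | 206 | 150/205 = 73.2% |

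Counting study days instead of elapsed days gives 151/206 = 73.3% for the last row.

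**Scheduled assessments on or after Day 56, participant followed to Day 206**
- 24-hour visits: 9 of 11 by nominal day. The Day 56 visit has a ±2 day window, so it can fall on Day 54 or 55, which leaves 8.
- Post-dose safety laboratory panels: 2 of 4 (Days 84 and 206).
- Vital-sign days after Day 2: 2 of 3 (Days 84 and 206).
- Post-dose physical examinations: the only scheduled one, at EoS.

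**Missing-date rule, hypothetical example.** Suppose dosing on 1 January of a non-leap year. Day 56 is 25 February (31 + 25) and 1 March is Day 60 (31 + 28 + 1). An AE dated to March with the day unknown starts on Day 60 at the earliest. Its partial date does not place it before treatment, so it is assigned to the on-treatment period and counted. An AE fully dated 1 March is not counted.

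**The case against.** The strongest reply is that this is a declared, reasoned choice with little practical loss. SAP 7.1 states the departure and its reason, SAP 3.0 says the SAP supersedes the protocol's statistical considerations, and neither document sets a standard for how many half-lives an AE table must cover. The trial is small, open-label and single-arm, with no hypothesis tests. All AEs are listed with non-TEAEs flagged, and all SAEs, deaths and AEs leading to discontinuation are listed. Chemistry, hematology and vital signs are summarised by scheduled time, so Days 84 and 206 are included. Most of this stands, and it limits the harm to the summary counts. It does not restore the endpoint tables.

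A second reply is that 73% measures calendar time, not AEs. Exposure is a single dose, observation is continuous only to Day 29, and AEs may cluster early. That is right: 73% is a maximum share of follow-up time and should be read as nothing more.

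Third, the overview in 17.1.1 names SAEs and discontinuations due to AEs without calling them treatment-emergent, so those rows might not be time-limited. The opening sentence of 17.1.1 covers all AE summaries, and Table 14.3.1.1 is titled as an overview of TEAEs, so the restrictive reading is the one the text supports. A clarifying phrase would still help.

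Finally, the missing-date problem needs an unusual record and errs towards counting too much. That makes it small, but the rule is still inconsistent with the window it serves.

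**Conclusion.** The concern holds and should be fixed. As written, Tables 14.3.1.1 to 14.3.1.4 omit AEs with onset on or after Day 56, whatever their relatedness or seriousness, while the protocol's TEAE definition and AE recording run to EoS/ET. The omitted share of post-dose time ranges from 0% (last 24-hour visit on Day 35 or 42) to 73% (follow-up to Day 206). It depends only on when collection ends for each participant, using nominal visit days. The number of AEs affected cannot be derived from the documents. The missing-date rule is inconsistent with the Day 56 cut-off regardless of whether Day 56 is a good choice. The PK and mass-balance endpoints are unaffected, and no AE is lost from the listings.

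**What to change.** 1. Add an overview table and one summary by system organ class and preferred term, with severity and relatedness, of all AEs with onset or worsening from dosing through EoS/ET, following the protocol definition. If the Day 56 tables are kept, label them as an early-period summary and state which period the SAE and discontinuation rows cover.
2. Amend the missing-date rule in SAP 17.1.1 so that an AE whose partial date shows onset on or after Day 56 is not assigned to the Day 56 window.

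The cost is one extra analysis flag, two added summaries and a sentence or so of SAP wording, with no new data. The drawback is that more late background AEs will be counted; the relatedness recorded for each AE helps to separate these.

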17.1.2 Deaths and Serious Adverse Events

A listing of deaths and a listing of all SAEs will be provided by participant.

17.1.3 Laboratory Data

Clinical laboratory data will be presented using units from the study data tabulation model (SDTM) Controlled Terminology.

All laboratory data will be listed. A separate listing of out-of-range values will also be provided. Normal ranges will be used directly from the clinical laboratory.

Clinical laboratory results outside the reference range will be flagged. In case the out of reference range values were considered clinically significant by the Investigator, this will also be indicated in the listings as well as in the AE listing. Comments with regard to the laboratory test results will be shown in a separate listing.

Results of continuous parameters recorded as being below or above a detection limit (e.g. "<1.5", ">800") will be imputed in the calculation of descriptive statistics as the detection limit plus or minus one precision unit of the respective parameter (in the above example: 1.4 and 801). Listings will present the values before imputation.

Descriptive statistics summarizing continuous laboratory results of clinical chemistry, hematology (observed and derived changes from baseline) and coagulation (observed) by scheduled time will be included.

